#### 1. SAEs

documentation

Serious adverse events (SAEs) for studies where the SCCC DSMC is the DSMC of record require reporting to the DSMC coordinator within 5 working days of PI awareness, or as described in the protocol.

#### 2. Unanticipated Problems Involving Risks to Subjects or Others (UPIRSOs)

Local Serious Adverse Event UPIRSOs require reporting to the UTSW IRB within 48 hours of PI awareness of the event (life threatening or fatal events experienced by subjects enrolled by the investigator(s) under UTSW IRB jurisdiction).

Local UPIRSOs (non-serious events experienced by subjects enrolled by the investigator(s) under UTSW IRB jurisdiction) require reporting to the UTSW IRB within 5 business days of PI awareness of the event.

External UPIRSOs including those that occur as non-local events require reporting to the UTSW IRB within 10 working days of PI awareness of the event.

For further guidance for Investigators regarding safety reporting requirements for INDs and BA/BE studies, refer to FDA Draft Guidance document: http://www.fda.gov/downloads/Drugs/GuidanceComplianceRegulatoryInformation/GuidanceS/UCM227351.pdf

# 7.6 Steps to Determine If an Adverse Event Requires Expedited Reporting to the SCCC DSMC and/or HRPP.

Step 1: Identify the type of adverse event using the NCI Common Terminology Criteria for Adverse Events (CTCAE v4).

Step 2: Grade the adverse event using the NCI CTCAE v4.

Step 3:Determine whether the adverse event is related to the protocol therapy Attribution categories are as follows:

- Definite The AE is clearly related to the study treatment.
- Probable The AE *is likely related* to the study treatment.
- Possible The AE may be related to the study treatment.
- Unrelated The AE is clearly NOT related to the study treatment.

Note: This includes all events that occur within 30 days of the last dose of protocol treatment. Any event that occurs more than 30 days after the last dose of treatment and is attributed (possibly, probably, or definitely) to the agent(s) must also be reported accordingly.

Step 4: Determine the prior experience of the adverse event.

Expected events are those that have been previously identified as resulting from administration of the agent. An adverse event is considered unexpected, for expedited reporting purposes only, when either the type of event or the severity of the event is not listed in:

- the current known adverse events listed in the Agent Information Section of this protocol;
- the drug package insert;
- the current Investigator's Brochure

#### 7.6.1 Reporting SAEs and UPIRSOs to the Simmons Comprehensive Cancer Center (SCCC) Data Safety Monitoring Committee (DSMC)

All SAE/UPIRSOs at all sites, which occur in research subjects on protocols for which the SCCC is the DSMC of record require reporting to the DSMC regardless of whether IRB reporting is required. All SAEs/UPIRSOs occurring during the protocol-specified monitoring period should be submitted to the SCCC DSMC within 5 business days of the PI or delegated study team members awareness of the event(s). In addition, for participating centers other than UTSW, local IRB guidance should be followed for local reporting of serious adverse events.

The UTSW study team is responsible for submitting SAEs/UPIRSOs to the SCCC DSMC Coordinator. Hardcopies or electronic versions of the eIRB Reportable Event report; FDA Form #3500A forms, or other sponsor forms, if applicable; and/or any other supporting documentation available should be submitted to the DSMC Coordinator. The DSMC Coordinator forwards the information onto the DSMC Chairman who determines if immediate action is required. Follow-up eIRB reports, and all subsequent SAE/UPIRSO documentation that is available are also submitted to the DSMC Chair who determines if further action is required. (See Appendix III of the SCCC DSMC Plan for a template Serious Adverse Event Form which may be utilized when a sponsor form is unavailable and SAE submission to the eIRB is not required).

If the event occurs on a multi-institutional clinical trial coordinated by the UTSW Simmons Comprehensive Cancer Center, the DOT Manager or lead coordinator ensures that all participating sites are notified of the event and resulting action, according to FDA guidance for expedited reporting. DSMC Chairperson reviews all SAEs/UPIRSOs upon receipt from the DSMC Coordinator. The DSMC Chairperson determines whether action is required and either takes action immediately, convenes a special DSMC session (physical or electronic), or defers the action until a regularly scheduled DSMC meeting.

Telephone reports to: (Investigator/study team: Insert names and phone numbers for required notifications)

[name] [contact]

Written reports to: (Investigator/study team: Insert names, fax numbers, an addresses for required notifications)

UTSW SCCC Data Safety Monitoring Committee Coordinator Email: [contact] [contact] or deliver to BLB.306

UTSW Institutional Review Board (IRB) Submit a Reportable Event via eIRB with a copy of the final sponsor report as attached supporting documentation

# Reporting Unanticipated Problems Involving Risks to Subjects or Others (UPIRSOs) to the UTSW HRPP/IRB

UTSW reportable event guidance applies to all research conducted by or on behalf of UT Southwestern, its affiliates, and investigators, sites, or institutions relying on the UT Southwestern IRB. Additional reporting requirements apply for research relying on a non-UT Southwestern IRB.

According to UTSW HRPP/IRB policy, UPIRSOs are incidents, experiences, outcomes, etc. that meet **ALL three (3)** of the following criteria:

- Unexpected in nature, frequency, or severity (i.e., generally not expected in a subject's underlying condition or not expected as a risk of the study; therefore, not included in the investigator's brochure, protocol, or informed consent document),AND
- 2. Probably or definitely related to participation in the research, AND
- Suggests that the research places subjects or others at a greater risk of harm (including physical, psychological, economic, or social harm) than was previously known or recognized. Note: According to OHRP, if the adverse event is serious, it would always suggest a greater risk of harm.

For purposes of this policy, UPIRSOs include unanticipated adverse device effects (UADEs) and death or serious injury related to a humanitarian use device (HUD).

UPIRSOs must be promptly reported to the UTSW IRB within 5 working days of PI awareness.

For research relying on a non-UT Southwestern IRB (external, central, or single IRB):

Investigators relying on an external IRB who are conducting research on behalf of UT Southwestern or its affiliates are responsible for submitting LOCAL UPIRSOs to the UT

Southwestern IRB within 5 working days of PI awareness. Investigators must report to their relying IRB according to the relying IRB's policy. In addition, the external IRB's responses or determinations on these local events must be submitted to the UT Southwestern IRB within 10 working days of receipt.

Events NOT meeting UPIRSO criteria:

Events that do NOT meet UPIRSO criteria should be tracked, evaluated, summarized, and submitted to the UTSW HRPP/IRB at continuing review.

For more information on UTSW HRPP/IRB reportable event policy, see https://www.utsouthwestern.edu/research/research-administration/irb/assets/policies-combined.pdf.

# 7.7 Reporting Requirements for Adverse Events

- 7.4.4 Expedited Reporting
  - The Principal Investigator must be notified within 24 hours of learning of any serious adverse events, regardless of attribution, occurring during the study or within 30 days of the last administration of the study drug.
  - Suspected adverse reactions will also be reported to Prometheus Laboratories. A copy of any SAE report submitted to any IRB must be sent to Prometheus Laboratories. If the "IL-2" is a suspect or co-suspect drug reported on the FDA Form 3500A MedWatch report, Prometheus Laboratories also requests a courtesy copy of the FDA Form 3500A MedWatch report that was submitted to the US Food and Drug Administration, via email or fax, to Drug Safety and Pharmacovigilance at Prometheus Laboratories, Inc. provided below. Please also include your contact information.
    - Drug Safety Email: [contact]
    - Drug Safety [contact]
  - Suspected adverse reactions will also be reported to FDA at [name] or www.fda.gov/medwatch.
  - The IRB must be notified within 10 business days of "any unanticipated problems involving risk to subjects or others" (UPR/UPIRSO).

The following events meet the definition of UPR:

- 1. Any serious event (injuries, side effects, deaths or other problems), which in the opinion of the Principal Investigator was unanticipated, involved risk to subjects or others, and was possibly related to the research procedures.
- 2. Any serious accidental or unintentional change to the IRB-approved protocol that alters the level of risk.
- 3. Any deviation from the protocol taken without prior IRB review to eliminate apparent immediate hazard to a research subject.
- 4. Any new information (e.g., publication, safety monitoring report, updated sponsor safety report), interim result or other finding that indicates an unexpected change to the risk/benefit ratio for the research.

- 5. Any breach in confidentiality that may involve risk to the subject or others.
- 6. Any complaint of a subject that indicates an unanticipated risk or that cannot be resolved by the Principal Investigator.
- The FDA should be notified within 7 business days of any unexpected fatal or life-threatening adverse event with possible relationship to study drug, and 15 business days of any event that is considered: 1) serious, 2) unexpected, and 3) at least possibly related to study participation.

#### 7.5 Stopping Rules

The study will be stopped if the combination treatment of SABR and HD IL-2 in the interim annual analysis is determined to confer significantly increased Grade 3-5 toxicity as reported in the literature from the treatments performed alone.

# 8.0 DRUG INFORMATION

#### 8.1 HD IL-2

- Other names for the drug(s): Proleukin, Aldesleukin
- Classification type of agent: Cytokine, Antineoplastic Agent, Miscellaneous; Biological Response Modulator
- Mode of action: Immune-stimulator; Binds to IL-2-receptor and activates proliferation
  of lymphocytes. Aldesleukin is a human recombinant interleukin-2 product which
  promotes proliferation, differentiation, and recruitment of T and B cells, natural killer
  (NK) cells, and thymocytes; causes cytolytic activity in a subset of lymphocytes and
  subsequent interactions between the immune system and malignant cells; can
  stimulate lymphokine-activated killer (LAK) cells and tumor-infiltrating lymphocytes
  (TIL) cells.
- Storage and stability: Refrigerator at 2° to 8°C (36° to 46°F). Avoid exposure to heat and light. Stability after reconstitution—24 hours.
- Protocol dose: 600,000 U/kg q8h up to 14 doses. Please see Appendix B.
- Preparation: PROLEUKIN is supplied as a sterile, white to off-white, lyophilized cake in single-use vials intended for intravenous (IV) administration. When reconstituted with 1.2 mL Sterile Water for Injection, USP, each mL contains 18 million IU (1.1 mg) PROLEUKIN, 50 mg mannitol, and 0.18 mg sodium dodecyl sulfate, buffered with approximately 0.17 mg monobasic and 0.89 mg dibasic sodium phosphate to a pH of 7.5 (range 7.2 to 7.8).
- Route of administration for this study: IV infusion over 15 minutes
- Incompatibility: Reconstitution and dilution procedures other than those recommended may result in incomplete delivery of bioactivity and/or formation of biologically inactive protein. Use of Bacteriostatic Water for Injection or Sodium Chloride Injection 0.9% should be avoided because of increased aggregation. Proleukin must not be mixed with other medicinal products except those mentioned in section 6.6. It is recommended that devices or administration sets containing in-line

filters are not used for delivery of Proleukin. Bioassays have shown significant loss of aldesleukin when filters are used.

- Availability: Commercially available from Novartis.
- Side effects:

**Cardiovascular**: Hypotension (71%: grade 4: 3%), peripheral edema (28%). tachycardia (23%), edema (15%), vasodilation (13%), supraventricular tachycardia (12%; grade 4: 1%), cardiovascular disorder (11%; includes blood pressure changes, HF and ECG changes). Central nervous system: Chills (52%), confusion (34%; grade 4: 1%), fever (29%; grade 4: 1%), malaise (27%), somnolence (22%), anxiety (12%), pain (12%), dizziness (11%). Dermatologic: Rash (42%), pruritus (24%), exfoliative dermatitis (18%). Endocrine & metabolic: Acidosis (12%; grade 4: 1%), hypomagnesemia (12%), hypocalcemia (11%). Gastrointestinal: Diarrhea (67%; grade 4: 2%), vomiting (19% to 50%; grade 4: 1%), nausea (19% to 35%), stomatitis (22%), anorexia (20%), weight gain (16%), abdominal pain (11%). Hematologic: Thrombocytopenia (37%; grade 4: 1%), anemia (29%), leukopenia (16%). **Hepatic**: Hyperbilirubinemia (40%; grade 4: 2%), AST increased (23%; grade 4: 1%). Neuromuscular & skeletal: Weakness (23%) **Renal:** Oliguria (63%; grade 4: 6%), creatinine increased (33%; grade 4: 1%) **Respiratory:** Dyspnea (43%; grade 4: 1%), lung disorder (24%; includes pulmonary congestion, rales, and rhonchi), cough (11%), respiratory disorder (11%; includes acute respiratory distress syndrome, infiltrates and pulmonary changes). **Miscellaneous:** Antibody formation (66% to 74%), infection (13%; grade 4: 1%)

• Nursing implications: Close monitoring in ICU setting.

# 9.0 CORRELATIVES/SPECIAL STUDIES

The goal of the planned laboratory correlative studies is to measure the induced immune response to patient's pre-treatment tumor tissue antigens (see section 1.5 for detail). In addition, the correlative studies will evaluate the immune response generated by the regiment. The submission of collected whole blood before, during and post treatment as indicated in Section 5 is mandatory and will be performed at baseline, during RT (one hour after first SABR fraction), after HD IL-2 cycle 2, at 8 weeks, 6 months and 1 year. Biopsy specimen of metastatic sites prior to initiation of treatment is required if previous biopsy of metastatic site within six months with adequate review of slides is not performed or available, in which case it is optional. If the patient participated in protocols [such as the Urology Tissue Repository Protocol (STU 032011-187)] or procedures and the tissue confirming kidney cancer diagnosis is in storage and available at UTSW Medical Center or an outside institution, the study team may request a tissue sample. The 8wks post-treatment biopsy is optional.

# 9.1 Sample Collection Guidelines

Samples will be labeled with the subject's de-identified study number and collection date and delivered for analysis during regular business hours to: NC7: 208; Attn [name]

**9.1.1 Whole blood sample:** Patient's whole blood will be collected in EDTA (Lavender top) tubes for ~ 100 ml at baseline, during RT (one hour after first SABR fraction), post HD IL-2, at 8 week and at 24 week (+/- 2 weeks) and at 1 year starting from the first day of study registration for immunologic assays. In addition, 10 ml will be collected in anti-coagulant-free tubes (Red top) for the collection of sera. The

only exception is the blood collection one hour post first SABR fraction which will be for 20ml in EDTA and 20 ml in anti-coagulant-free tubes The blood will immediately be processed (within 2 hours) by centrifugation (1000g, 15min, 4 °C), collecting the supernatant and freezing at -80 °C in 5 aliquots for future experiments. The pellet will be re-suspended in PBS and PBMC will be isolated using standard protocol. Briefly, the cell suspension will be carefully placed on 10ml polystyrene tube containing 1ml ficoll and centrifuged (400g, 30min, RT). Collect the PBMC region from the ficoll and washed 3x with PBS. Count and freeze cells in 5 aliquots with 10%DMSO 90%FBS in -80°C.

- **9.1.2 Tumor Biopsy Sample:** A CT-guided biopsy of tumor lesion consisting of 4-5 18G needle cores is recommended at the time of registration of the patients to the study. If the patient participated in protocols [such as the Urology Tissue Repository Protocol (STU 032011-187)] or procedures and the tissue confirming kidney cancer diagnosis is in storage and available at UTSW Medical Center or an outside institution, the study team may request a tissue sample. A second biopsy at 8 weeks (+/- 2 week) after the last HD IL-2 treatment is elective.
  - 9.1.2.1 Initial required biopsy: 3-4 core biopsies will be processed as routine diagnostic specimens by Pathology for the purpose of diagnosis and Immumo-histochemistry (IHC). After on site adequacy check using touch imprint slides, the cores will be fixed in 10% buffered formalin for up to 8 hours and processed routinely to obtain formalin fixed paraffin embedded blocks. Eight, 3-micron thick sections will be cut. The first and last sections will be stained with hematoxylin and eosin (H&E) stain to evaluate the presence, extent, and grade of renal carcinoma. The remaining sections will be used to perform immunohistochemical staining if needed. (see section 9.2 for IHC detail). Two additional cores will be placed in normal saline on wet ice and brought to NC9.208 ([name]) for generation of tumor lysates to be used as a source of antigen in the immunoassays. The biopsy cores will be chopped into minute pieces. Small volume of normal saline is added and the mixture is passed through a 19G needle, attached to a 5 ml syringe, several times, until the passage of the mixture occurred without difficulty. The process is repeated with 21G, 23G, and if possible 25G needle. The entire mixture is placed in liquid nitrogen until frozen, and then thawed in a water bath at 42°C. The freezing and thawing is repeated for a total of five times. The sample is passed through another 23G or 25G needle to disperse any clumps. The sample is then centrifuged at high speed, the supernatant collected, protein concentration measured using NanoDrop2000 and frozen at -80 °C in 5 aliquots.
  - **9.1.2.2 8 week Elective Biopsy:** One core from the biopsy will be processed by pathology to generate slides for histology and IHC. The second and third core will be placed in normal saline on wet ice and brought to NC9.208 ([name]) for processing for flow cytometry of cells. The tumor tissue is first cut into small pieces and incubated in PBS containing DNAse I 1mg/ml (Roche Diagnostics, Indianapolis, IN) and Collagenase 2mg/ml (Fisher Scientific, Pittsburgh, PA) for 1h at 37oC. The lysate is then passed through cell strainer in PBS and washed 2x in 10ml of PBS

followed by RBC lysis buffer. The cells are then frozen in 4 aliquots with 10%DMSO 90%FBS in -80°C for future flow cytometry analysis.

# 9.2 Assay Methodology

- 9.2.1 Elispot: IFN-γ ELISpot assays will be performed according to manufacturer's protocol using a commercial ELISpot kit (MabTECH). Briefly, 96 well plates are coated overnight with 0.015 mg/ml of an anti-human IFN-g monoclonal antibody. PBMC from patients will be incubated in triplicates wells and stimulated in the presence of either PA2024 (10µg/ml), protein lysate from patient biopsy (50µg/ml) or 5 ng/ml PMA and 0.5 ng/ml ionomycin as positive control and albumin as negative control. For ELISPOT assays, plates are incubated for 48 hours, washed, probed with biotinylated anti-IFNg, further washed, and then incubated with streptavidin alkaline phosphatase. Spot development is achieved with 5-bromo-4-chloro-3-indolyl phosphate/nitroblue tetrazolium (BCIP/NBT; Invitrogen) and spots are enumerated by an automatic ELISpot reader.
- **9.2.2 ELISA**: In this procedure, patient tumor tissue lysate is first adsorbed to an EIA 96 well microplate (Fischer). Patient plasma is then added to each well as a source of primary antibody and serially diluted. After extensive washes, detection enzyme (HRP)-linked anti-human mAb is then added to each well and allowed to bind. Appropriate substrate is then added to each well and color development occurs within 5-60 min. UV Microplate Reader will be used to read the plates
- 9.2.3 H-thymidine Proliferation Assay: PBMC from patients will be incubated in a similar manner as above for five days at 37 °C then overnight with 0.5 mCi tritiated H-thymidine, harvested onto a glass-fiber filter using a 96-well FilterMate cell harvester. The radioactivity of the H-thymidine is detected by a direct betaplate counter. The degree of antigen-specific clonal T cell expansion will be expressed as a stimulation index (SI) of the ratio of H-thymidine incorporation by cells incubated with patient tumor lysate compared with media controls. An alternate method utilizing FACS analysis with carboxy fluorescein diacetate succinimidyl ester (CFSE) is also available [108].
- **9.2.4** Chromium Release Cytotoxicity Assays: For cell-mediated cytotoxicity analysis, A 50 μl sample of Cr-labeled target cells (Caki-2 and ACHIN human renal cancer cells) is mixed with 100μl of effector cells (patient PBMC) at various target to effector ratio (E:T ratios). After centrifugation at 100 X G, the cells are incubated for 2 hr at 37°C. The radioactivity of culture supernatant is measured using a gamma counter and percentage of cytotoxicity is calculated. For antibody-dependent cytotoxicity analysis this procedure will be performed with patient's plasma instead of PBMC and the percentage of cytotoxicity is calculated in similar manner. An alternate and non-radioactive labeling method utilizes GAPDH enzyme release from lysed cells called Bioluminescence Non Radioactive Cytotoxicity Assay (aCella-TOX, T Cell Technology, INC) [109, 110].
- **9.2.5** Flow cytometric analysis (FACS): For FACS analysis of cell-surface molecules, the cell samples are stained with fluorescent dye conjugated monoclonal antibodies against the selected markers on ice followed by fixation with 4% paraformaldahyde. Data are acquired on a LSRII (BD Biosciences) and analyzed using FACSDiva software (BD Biosciences). The PBMC of each patient before and after treatment will be analyzed to identify the relative sub-population of CTLs,

regulatory T-Cells, effector memory T cells, MDSCs, neutrophils and NK cells utilizing appropriate cell surface markers (see section 1.5).

- 9.2.6 **Immunohistochemical staining (IHC):** Standard immunohistochemistry staining procedure for will be performed using the Benchmark XT automated stainer (Ventana) for both antibodies. Briefly, formalin-fixed, paraffin-embedded tissue sections will be cut at 3-4 micron and air-dried overnight. The sections will be deparaffinized, rehydrated, and subjected to heat-induced epitope retrieval. Sections will then be incubated with appropriate primary antibody. For signal detection, ultraView universal detection system (Ventana) will be used. The slides will be developed using 3-3'-diaminobenzidine chromogen and counterstained with hematoxylin. Appropriate positive and negative controls will be utilized for each run of immunostains. The evaluation of the immunostaining will be carried out by a genitourinary pathologist without knowledge of any clinicopathologic data. Only nuclear reactivity will be considered positive. An H score will be assigned as the product of average intensity of staining (0 for negative, 1 for weakly positive, 2 for moderately positive, and 3 for strongly positive) and extent of immunoexpression (0-100% percentage of cells staining). In addition, Dualantibody ISH will be performed to identify and analyze TILs, CTL (CD3+,CD8+), Tregs (CD4+FoxP3), DC (CD11c), NK/T (CD3+, CD1d), neutrophils (CD11b, Ly6G} and MDSC (CD14+,CD11b) in the tumor tissue before and after treatment, when available (see section 1.5).
- 9.2.7 Serum Cytokine Analysis: Multiplex cytokine analysis in patient's plasma will be performed in precoated 96 well plates (Human TH1/TH2 10 plex ultrasensitive assay, Meso Scale Discovery - MSD, Maryland, USA) according to manufacturer's instructions. 25 µL of diluent 2 is dispersed into each well. The plate is sealed and incubated by vigorous horizontal shaking for 30 minutes at RT. 25 μL of the patient plasma is added per well and all samples measured in triplicates. Plates are sealed and incubated by vigorous horizontal shaking for two hours at RT. Plates are washed three times with 0.05% Tween 20 in PBS . 25 µL of 1× detection antibody solution is placed per well and sealed plates are incubated by vigorous horizontal shaking for two hours at RT. Plates are washed three times with 0.05% Tween 20 in PBS. 150 µL of 2× Read Buffer T is added to each well. Plates are analysed using the MSD SECTOR Imager 2400 and Discovery Workbench 3.0 software (both from Meso Scale Discovery, USA). The mean value of two wells is taken as the recorded reading, provided that the coefficient of variation (CV) was less than 10%. Concentrations recorded lower than the standard curve are kept as absolute values. For purposes of logarithmic analysis, readings of 0 are adjusted to 0.01 pg/ml. The following cytokines will be measured before and after treatment for each patients: Th1/Th2/Th17 cytokines, IFN-y, IL-1β, IL-2, IL-4, IL-5, IL-8, IL-10, IL-12p70, IL-13, IL-17 TNF-α; proinflammatory cytokines: GM-CSF, IFN-γ, IL-1β, IL-2, IL-6, IL-8, IL-10, IL-12p70, TNF-α; Chemokines: Eotaxin, MIP-1β, TARC, IP-10, IL-8, MCP-1, MCP-4 and others including IL-6, TGF- $\beta$  and HMGB1 (see section 1.5).
- **9.2.8** Western-blot/Immuno-blot: Caki-2 and ACHIN human renal cancer cells lysate will be used to perform immune-blott using plasma collected from patients before and after treatment. The Caki-2 and ACHIN cell 10^6 cells/mL will be lysed in immunoprecipitation assay buffer on ice for 30 min. Standard western blott methodology will be utilized. Briefly, 400 μg of protein will be separated using premade gradient 4% to 12% Bis-Tris gels (Invitrogen, Burlington, ON, Canada) and transferred to nitrocellulose. Patient sera/plasma will be diluted 1/500 in Blotto (5% dry milk powder; 0.1% Tween 20; 50 mmol/L Tris; 150 mmol/L NaCl) and

incubated with nitrocellulose membranes for 1 h at room temperature using a multichannel immuoblotting device (Mini Protean II Multiscreen, Bio-Rad, Missassauga, ON, Canada). The membrane will then incubated for 1 h at room temperature with horseradish peroxidase–conjugated goat anti-human IgG (H+L; Jackson ImmunoResearch, West Grove, PA) diluted 1/10,000 in Blotto and visualized by enhanced chemiluminescence.

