Enhancements of increased cytotoxicity to renal cancer cells can be measured by cytotoxicity assays. Antibody-dependent cell-mediated cytotoxicity (ADCC) measures the cell-killing ability of certain lymphocytes that require the target cell to be marked by an antibody and thus measures the humeral response [28]. On the other hand, lymphocyte-mediated cytotoxicity assay will measure the formation of tumor-specific CTLs among the lymphocytes collected from patients with the controls being lymphocytes collected from the same patients before SABR and before HD IL-2. Since it is not practical or feasible to obtain sufficient quantities of tumor cells from each patients to assess a quantitative cytotoxicity by these assays, established allogenic human human renal cancer cell line Caki-2 and ACHIN will be used for this purpose. It is a generally accepted principle of tumor immunology that there will be many common tumor antigens between different patient tumors of same site origin, and therefore tumor cell lines as well [28]. In fact, the tumor antigens (PSA, CEA, CA 19-9 etc.) that are in clinical practice are reported to be present in a significant portions of patients of the respective tumor site. This concept of commonality of tumor antigens between allogenic tumor cell lines and patients is put into clinical practice by the GVAX anti-tumor vaccine which is currently in early phase clinical trials for pancreatic, melanoma and renal cancer [62, 63]. GVAX consists of multiple human tumor cell lines of the respective site, that is modified to express GM-CSF, and killed with radiation prior to injection in patients. The presence of common tumor antigens in the cell lines and patient's tumors, leads to induction of an immune response. The LNCaP and PC-3 cell lines has been shown to express many of the common renal cancer antigens, and therefore, is an appropriate surrogate to be used instead of patient's own cells and has been used in similar in vitro cytotoxicity assays [64-68].

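### The antibody-dependent cytotoxicity assay in section 9.2.4 names no effector cells, so as written it cannot measure ADCC as section 1.5 defines it

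*Combined protocol and SAP*

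**What the plan says.** Section 1.5 (Correlative Studies) plans two cytotoxicity readouts. One is the lymphocyte-mediated assay for tumour-specific T cells. The other is ADCC, which in the protocol's words "measures the cell-killing ability of certain lymphocytes that require the target cell to be marked by an antibody" and which the section uses as a measure of the humoral response. Both are to use the Caki-2 and ACHIN renal cancer lines as targets, because patients cannot supply enough tumour cells.

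Section 9.2.4 gives the method. For the cell-mediated version, 51Cr-labelled targets are mixed with a volume "of effector cells (patient PBMC) at various target to effector ratio (E:T ratios") and incubated for 2 hours. The readout is then described: "The radioactivity of culture supernatant is measured using a gamma counter and percentage of cytotoxicity is calculated". The antibody-dependent version is defined by one change: "For antibody-dependent cytotoxicity analysis this procedure will be performed with patient's plasma instead of PBMC". Percent cytotoxicity is calculated in the same way. A non-radioactive labelling method is offered as an alternative.

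Section 9.1.1 covers the samples. "Patient's whole blood will be collected in EDTA (Lavender top) tubes", and anticoagulant-free tubes are drawn as well for serum. After centrifugation the supernatant is frozen. For the cells, "The pellet will be re-suspended in PBS and PBMC will be isolated using standard protocol".

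**The concern.** ADCC in the protocol's own sense needs three things in the well: a labelled target, antibody bound to it, and a lymphocyte to do the killing. Exchanging the PBMC for plasma supplies the antibody but takes away the lymphocyte. This is a stated rule that does not fit the stated purpose, not a detail left to a laboratory manual.

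Section 1.5 intends each arm of the immune response to be examined with its own assay. ELISA and immunoblot show that antibody binds tumour antigen; ADCC is the planned test of whether such antibody can direct cell killing. If the assay is run as written, a flat result could be misread as absence of functional antibody, and a positive result could be misread as ADCC. The stored material is finite, since plasma and PBMC are each frozen in 5 aliquots, so the wording is best settled before samples are used.

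**Working it through.** The plan states no figure for this assay, so the check is a comparison of the sections followed by a short piece of algebra.

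**Step 1. What each version contains.**

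| Component | Needed for ADCC (section 1.5) | Cell-mediated version (9.2.4) | Antibody-dependent version (9.2.4) |
|---|---|---|---|
| Labelled target cells | yes | yes | yes |
| Patient antibody (plasma) | yes | not added | yes |
| Effector lymphocytes | yes | patient PBMC | none named |

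Section 9.1.1 confirms that the plasma is not a source of cells: it is the spun supernatant, and PBMC are recovered from the pellet. With PBMC removed, the effector-to-target ratio that 9.2.4 varies has no meaning. The alternative labelling method changes how lysis is detected and adds no effectors.

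**Step 2. What such a well would read.** Section 9.2.4 gives no formula for percent cytotoxicity and no spontaneous-release or maximum-release control. Assume the usual form, with E, S and M the experimental, spontaneous and maximum release:

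specific lysis = (E − S) / (M − S)

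- Background subtracted, no non-cellular lysis: E = S, so the reading is 0 / (M − S) = 0%.
- Background not subtracted: the reading is S / M. An assumed spontaneous release of 5% to 20% of maximum would read 5% to 20%.
- Plasma lyses a fraction c of targets without cells, for example through complement: E = S + c(M − S), so the reading is c(M − S) / (M − S) = c.

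The reading therefore depends on choices the protocol does not state. In all three cases the contribution of antibody-dependent cell-mediated killing is nil, because no cell is present to carry it out.

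**Step 3. Where the result would be used.** Section 2.4.4 defines the immune-response endpoint by ELISpot, T-cell proliferation and ELISA. Section 11.3 plans analyses of ELISpot spots and the proliferation index. Neither names a cytotoxicity assay. What remains is the general immune-response objective (2.2.6) and the biomarker exploration (2.3.1), which names no particular assay.

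**The case against.** The strongest reply is that 9.2.4 may not describe ADCC at all. It speaks of antibody-dependent cytotoxicity, in contrast to the cell-mediated kind. Reference 109, cited there for the alternative label, names complement-mediated lysis in its title. On that reading, targets plus plasma is a coherent non-cellular assay and the conflict with section 1.5 is one of naming. This cannot be excluded. EDTA plasma makes complement lysis unlikely, but serum without anticoagulant is also collected, and the protocol uses plasma and serum loosely (9.2.7 is headed as a serum analysis but runs on plasma). The reading does not remove the inconsistency, however: section 1.5 explicitly calls the assay cell-mediated, so one of the two sections must change.

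A second reply is that the wording is shorthand for adding plasma to the effector cells. The text says that plasma takes the place of the PBMC. Even if addition was meant, the effector source would be unspecified, and here that matters. The immunologic rationale (1.4.1) says IL-2 treatment activates NK cells, so effectors drawn afresh at each visit could raise lysis after IL-2 without any new antibody.

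A third reply is that little depends on this assay. That stands, and it limits the weight of the point.

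A reader might also infer that the assay will read about zero at every visit, in up to 33 × 6 = 198 samples (the section 11.2 maximum times the six collections in 9.1.1), and that the trial would then falsely conclude that no antibody-dependent cytotoxicity was induced. The documents do not support this. The reading is not fixed without a formula and controls, no section assigns this assay to all six collections, and no such conclusion is among the planned analyses.

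**Conclusion.** The point holds in a limited form. Sections 1.5 and 9.2.4 disagree on what the assay contains, and the method as written cannot detect antibody-dependent cell-mediated killing. Whatever it shows, signal or none, could not be attributed to that mechanism. This follows from the text alone and needs no assumption about tube type, background correction or visit schedule.

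No numerical size can be put on it, because the documents give no expected reading and no schedule for this assay. Its reach is confined to the exploratory correlatives under 2.2.6 and 2.3.1, and only in part, since ELISA and immunoblot also address the humoral response. The conclusion assumes that no separate laboratory procedure supplies effector cells; the protocol refers to none for this step. The correction is still worth making because it is cheap and stored aliquots are limited.

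**What to change.** Rewrite the antibody-dependent step in 9.2.4 as follows:

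- Incubate labelled Caki-2 or ACHIN targets with the patient's plasma or serum as the antibody source, and add effector PBMC.
- Take the effectors from one constant source for all of a patient's visits: a single donor lot, or the patient's stored baseline PBMC if the aliquots suffice. Then only the antibody varies between visits.
- Include effector-only wells and plasma- or serum-only wells, and state the percent-cytotoxicity formula.
- Report ADCC as lysis with targets, plasma or serum and effectors, minus lysis with targets and effectors alone. The plasma- or serum-only wells show any non-cellular lysis.

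If a non-cellular assay is what was intended, give it a name that says so, specify the anticoagulant-free serum, and correct the description in section 1.5.

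The cost is small: a donor lot or one baseline PBMC aliquot per patient, a few control wells, and no additional patient sample. Before choosing the baseline option, check the cell yield, because the 5 PBMC aliquots also have to serve ELISpot, proliferation, cell-mediated cytotoxicity and flow cytometry.
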